5.3.1 Description of the Dosage Form

Lirilumab Injection 100 mg/Vial (10 mg/mL): Lirilumab injection has been developed to be used as an intravenous (IV) infusion for clinical studies. The drug product is a clear to opalescent, colorless liquid, which may contain few particles.

The 100-mg/vial presentation is contained in a 10-cc Type I flint glass vial, closed with 20-mm stoppers, and sealed with aluminum seals. Each vial of the drug product contains the labeled amount of lirilumab drug substance, sucrose, sodium phosphate monobasic, sodium phosphate dibasic, polysorbate 80 (PST), and water for injection. Diluted sodium hydroxide and/or hydrochloric acid solution may be added to adjust the pH to 7.0. A sufficient overfill is included in each vial to account for vial, needle, and syringe holdup.

5.3.2 Drug Product Preparation

Lirilumab injection is administered IV either undiluted (10 mg/mL) or diluted in NS to lirilumab concentrations as low as 0.5 mg/mL. The dosing solution is to be infused using a volumetric pump at the protocol-specific dose(s) and rate(s) through a non-di-2-ethylhexyl phthalate (DEHP) or DEHP IV infusion set with a 0.2 micron polyethersulfone in-line filter. The drug product is not to be administered as an IV push or bolus injection.

Care must be taken to ensure the sterility of the prepared solutions, as the drug product does not contain anti-microbial preservatives or bacteriostatic agents.

5.3.3 Recommended Storage and Use Conditions

Lirilumab injection should be stored refrigerated at 2°C to 8°C and protected from light and freezing. The administration of lirilumab infusions must be completed within 24 hours of preparation. If not used immediately, the infusion solution may be stored in a refrigerator at 2°C to 8°C (36°F to 46°F) for up to 20 hours, and at room temperature (20°C to 25°C, 68°F to 77°F) and room light for a maximum of 4 hours. The maximum 4-hour period under room temperature and room light conditions includes the product administration period. The solution in IV bag (diluted or undiluted) should not be shaken or frozen. Equilibration to room temperature is recommended for the infusion bag, drug product, or their combination prior to administration.

5.4 Pharmaceutical Properties and Formulation for Nivolumab:

5.4.1 Description of the Dosage Form

Nivolumab injection, 100 mg/10 mL (10 mg/mL): Nivolumab injection, 100 mg/10 mL (10 mg/mL) is a clear to opalescent, colorless to pale yellow liquid, which may contain light (few) particulates. The drug product is a sterile, non-pyrogenic, single-use, isotonic aqueous solution formulated at 10 mg/mL in sodium citrate, sodium chloride, mannitol, diethylenetriaminepentacetic acid (pentetic acid), and polysorbate 80 (Tween 80), at pH 6.0 and includes an overfill to account for vial, needle, and syringe holdup. It is supplied in 10-cc Type I flint glass vials, stoppered with butyl rubber stoppers and sealed with aluminum seals. The only difference between the two drug product presentations is the vial fill volume.

5.4.2 Drug Product Preparation

Nivolumab Injection, 100 mg/10 mL (10 mg/mL): Nivolumab injection is to be administered as an IV infusion through a 0.2 - 0.22 micron pore size, low-protein binding (polyethersulfone membrane) in-line filter at the protocol-specified doses and infusion times. It is not to be administered as an IV push or bolus injection. When the dose is based on patient weight (ie, mg/kg), nivolumab injection can be infused undiluted (10 mg/mL) or diluted with 0.9% Sodium Chloride Injection, USP or 5% Dextrose Injection, USP to protein concentrations as low as 0.35 mg/mL. When the dose is fixed (eg, 240 mg, 360 mg, or 480 mg flat dose), nivolumab injection can be infused undiluted or diluted so as not to exceed a total infusion volume of 120 mL.

During drug product preparation and handling, vigorous mixing or shaking is to be avoided.

Care must be taken to assure sterility of the prepared solution as the product does not contain any antimicrobial preservative or bacteriostatic agent. Nivolumab infusions are compatible with

polyvinyl chloride (PVC) or polyolefin containers and infusion sets, and glass bottles.

5.4.3 Recommended Storage and Use Conditions

Nivolumab Injection, 100 mg/10 mL (10 mg/mL): Vials of nivolumab injection must be stored at 2°C to 8°C (36°F to 46°F) and protected from light and freezing.

Undiluted Nivolumab Injection and Diluted Nivolumab Injection in the IV Container: The administration of nivolumab infusion must be completed within 24 hours of preparation. If not used immediately, the infusion solution may be stored under refrigeration conditions (2°C to 8°C, 36°F to 46°F) for up to 24 hours, and a maximum of 8 hours of the total 24 hours can be at room temperature (20°C to 25°C, 68°F to 77°F) and room light. The maximum of 8 hours under room temperature and room light conditions includes the product administration period.

5.5 General Concomitant Medication and Supportive Care Guidelines

Because there is a potential for interaction of IND Agents with other concomitantly administered drugs through the cytochrome P450 system, the case report form must capture the concurrent use of all other drugs, over-the-counter medications, or alternative therapies. The Overall PI should be alerted if the participant is taking any agent known to affect or with the potential to affect CYP450 isoenzymes.

5.5.1 Prohibited and/or Restricted Treatments

The following medications are prohibited during the study (unless utilized to treat a drug related adverse event):

- Immunosuppressive agents
- Immunosuppressive doses of systemic corticosteroids
- Any concurrent anti-neoplastic therapy (ie, chemotherapy, hormonal therapy, immunotherapy, extensive, non-palliative radiation therapy, or standard or investigational agents for treatment of NSCLC)

5.5.2 Other Restrictions and Precautions

Participants with a condition requiring systemic treatment with either corticosteroids (> 20 mg daily prednisone equivalent) or other immunosuppressive medications within 14 days of the first dose of study treatment are excluded. Inhaled or topical steroids, and adrenal replacement steroid doses > 20 mg daily prednisone equivalent, are permitted in the absence of active autoimmune disease.

5.5.3 Permitted Therapy

Participants are permitted the use of topical, ocular, intra-articular, intranasal, and inhalational corticosteroids (with minimal systemic absorption). Adrenal replacement steroid doses > 10 mg daily prednisone are permitted. A brief (less than 3 weeks) course of corticosteroids for prophylaxis (eg, contrast dye allergy) or for treatment of non-autoimmune conditions (eg, delayed-type hypersensitivity reaction caused by a contact allergen) is permitted.

5.6 Criteria for Taking a Participant Off Protocol Therapy

The following stopping rule will be used to monitor delays in salvage surgery due to excessive nivolumab and/or lirilumab-related toxicity: if 3 or more of the first 10 patients who begin protocol treatment experience treatment related toxicities which cause delays in definitive surgery, accrual to the trial will be suspended to further evaluate the events and decisions made regarding the overall status of the trial. If the true delay in surgery rate due to toxicity is 10% then the probability of suspending accrual is 7%; if the true rate is 20%, then the probability of suspending accrual is 32.2%; if the true delay in surgery rate due to toxicity is 30% then the probability of suspending accrual is 62%. Adverse events will be continuously monitored throughout the trial by the study team with decisions made accordingly regarding the study status and patient entry throughout the duration of the trial.

Any adverse event(s) (as outlined in Section 6.1) attributed to the study medication that result in a delay in the planned date of salvage surgery exceeding 14 days warrants removal of the patient from the study protocol treatment. Otherwise, therapy can be resumed in the adjuvant phase at the discretion of the treating physician or PI. Duration of therapy will depend on individual response, evidence of disease progression or recurrence and tolerance. In the absence of treatment delays in the adjuvant phase due to adverse event(s), treatment may continue for six cycles or until one of the following criteria applies:

- Disease progression or recurrence
- Intercurrent illness that prevents further administration of treatment
- Unacceptable adverse event(s) (see Section 6.2)
- Participant demonstrates an inability or unwillingness to comply with the medication regimen and/or documentation requirements
- Participant decides to withdraw from the protocol therapy
- General or specific changes in the participant's condition rendering the participant unacceptable for further treatment in the judgment of the treating investigator

Participants will be removed from the protocol therapy when any of these criteria apply. The reason for removal from protocol therapy, and the date the participant was removed, must be documented in the case report form (CRF). Alternative care options will be discussed with the participant.

An ODQ Treatment Ended Form will be filled out when a participant is removed from protocol therapy. This form can be found on the DF/HCC website at <http://www.dfhcc.harvard.edu/research/clinical-research-support/document-library-forms-sops-etc/>.

In the event of unusual or life-threatening complications, treating investigators must immediately notify the Overall PI, **[name] at [contact] or [contact].**

5.7 Duration of Follow Up

Participants, regardless if they receive the adjuvant therapy, will be followed for response (at the end of the window phase of the trial) and until first disease progression/recurrence and for survival for 5 years from point of salvage surgery (or from study registration if no salvage surgery was performed). Participants removed from protocol therapy for unacceptable adverse event(s) will be followed until resolution or stabilization of the adverse event.

5.8 Criteria for Taking a Participant Off Study

Participants will be removed from study when any of the following criteria apply:

- Patient completed required follow-up
- Lost to follow-up
- Withdrawal of consent for data submission
- Death

The reason for taking a participant off study, and the date the participant was removed, must be documented in the case report form (CRF).

For “Centralized Subject Registrations”, the research team submits a completed Off Study form to ODQ when a participant comes off study. This form can be found on the ODQ website or obtained from the ODQ registration staff.

For Decentralized Subject Registrations, the research team updates the relevant Off Treatment/Off Study information in OnCore.

6. DOSING DELAYS/DOSE MODIFICATIONS

There will be no dose reductions for nivolumab or lirilumab permitted. Doses of nivolumab or lirilumab may be interrupted, delayed, or discontinued depending on how well the participant tolerates the treatment. If a lirilumab dose is delayed beyond four weeks from the prior lirilumab dose, then subsequent lirilumab doses should be rescheduled, if needed, such that the patient receives both nivolumab and lirilumab at next visit

6.1 Administration both study drugs should be delayed for the following adverse events:

- Grade 2 non-skin, drug-related adverse event, with the exception of fatigue
- Grade 2 drug-related creatinine, AST, ALT and/or Total Bilirubin abnormalities
- Grade 3 skin, drug-related adverse event
- Grade 3 drug-related laboratory abnormality, with the following exceptions:
 - Grade 3 lymphopenia or asymptomatic amylase or lipase does not require dose delay
 - Grade \geq 3 AST, ALT, Total Bilirubin will require dose discontinuation

- Any adverse event, laboratory abnormality, or intercurrent illness which, in the judgment of the investigator, warrants delaying the dose of study medication.
Note: see Appendix C for guidelines on managing immune-related toxicities

Participants who require delay of nivolumab or lirilumab should be re-evaluated weekly or more frequently if clinically indicated and resume nivolumab or lirilumab dosing when re-treatment criteria (as described below) are met. Participants with a delay in dosing beyond 8 weeks should be considered for discontinuation of protocol treatment and discussed with the Overall PI.

Subsequent dosing may be re-started if subjects continue to meet laboratory criteria (baseline values). The investigator will determine if subsequent dosing is appropriate for subjects who have laboratory or clinical abnormalities that do not meet dose discontinuation criteria (described below). All related grade 2 toxicities should be discussed with the Overall PI, prior to subsequent dosing.

6.2 Administration of both study drugs should be permanently discontinued for the following adverse events:

- A grade 3 pneumonitis and grade 3 uveitis will require permanent discontinuation.
- Any grade 4 adverse event will require permanent discontinuation with the following exceptions:
 - Grade 4 electrolyte abnormalities that < 72 hours in duration
 - Grade 4 neutropenia < 5 days in duration
 - Grade 4 increase in amylase or lipase that is not associated with clinical or radiographic evidence of pancreatitis
 - Grade 4 lymphopenia < 5 days in duration

The consideration to re-initiate study therapy under these exceptions will be made on a case by case basis after considering the overall benefit/risk profile and in consultation with the Overall PI.

7. ADVERSE EVENTS: LIST AND REPORTING REQUIREMENTS

Adverse event (AE) monitoring and reporting is a routine part of every clinical trial.

7.1 Adverse Event Characteristics:

- **CTCAE term (AE description) and grade:** The descriptions and grading scales found in the revised NCI Common Terminology Criteria for Adverse Events (CTCAE) version 4.0 will be utilized for AE reporting. All appropriate treatment areas should have access to a copy of the CTCAE version 4.0. A copy of the CTCAE version 4.0 can be downloaded from the CTEP web site http://ctep.cancer.gov/protocolDevelopment/electronic_applications/ctc.htm.
- **Attribution** of the AE:
 - Definite – The AE is clearly related to the study treatment.
 - Probable – The AE is likely related to the study treatment.

- Possible – The AE may be related to the study treatment.
- Unlikely – The AE is doubtfully related to the study treatment.
- Unrelated – The AE is clearly NOT related to the study treatment.

7.2 Serious Adverse Events

A *Serious Adverse Event (SAE)* is any untoward medical occurrence that at any dose:

- Results in death
- Is life-threatening (defined as an event in which the participant was at risk of death at the time of the event; it does not refer to an event which hypothetically might have caused death if it were more severe)
- Requires inpatient hospitalization or causes prolongation of existing hospitalization (see **NOTE** below)
- Results in persistent or significant disability/incapacity
- Is a congenital anomaly/birth defect
- Is an important medical event (defined as a medical event(s) that may not be immediately life-threatening or result in death or hospitalization but, based upon appropriate medical and scientific judgment, may jeopardize the subject or may require intervention [eg, medical, surgical] to prevent one of the other serious outcomes listed in the definition above.) Examples of such events include, but are not limited to, intensive treatment in an emergency room or at home for allergic bronchospasm; blood dyscrasias or convulsions that do not result in hospitalization.)
- Suspected transmission of an infectious agent (eg, pathogenic or nonpathogenic) via the study drug is an SAE.

Although pregnancy, overdose, potential drug-induced liver injury (DILI), and cancer are not always serious by regulatory definition, these events must be handled as SAEs.

Any component of a study endpoint that is considered related to study therapy should be reported as an SAE (eg, death is an endpoint, if death occurred due to anaphylaxis, anaphylaxis must be reported).

7.3 Expected Toxicities

Expected adverse events are those that have been previously identified as resulting from administration of the agent. For the purposes of this study, an adverse event is considered expected when it appears in the current adverse event list in the Investigator's Brochure or is included in the informed consent document as a potential risk. Most common adverse events or expected toxicities are listed below. Details are found in the respective IBs. Management of expected toxicities is described in Appendix C.

Most common adverse reactions (>20%) related to nivolumab alone were: fatigue, rash, musculoskeletal pain, pruritus, diarrhea, nausea, asthenia, cough, dyspnea, constipation, decreased appetite, back pain, arthralgia, upper respiratory tract infection, pyrexia.

The most common adverse reactions (>5%) related to lirilumab alone were: asthenia, fatigue, pruritus, infusion-related reaction, chills, and neutropenia.

The most common adverse reactions (>10%) related to nivolumab in combination with lirilumab were: fatigue, pruritus, infusion-related reaction, and rash.

The following hospitalizations are not considered SAEs in BMS supported clinical studies:

- A visit to the emergency room or other hospital department < 24 hours, that does not result in admission (unless considered an important medical or life-threatening event)
- Elective surgery, planned prior to signing consent
- Admissions as per protocol for a planned medical/surgical procedure
- Routine health assessment requiring admission for baseline/trending of health status (eg, routine colonoscopy)
- Medical/surgical admission other than to remedy ill health and planned prior to entry into the study. Appropriate documentation is required in these cases.
- Admission encountered for another life circumstance that carries no bearing on health status and requires no medical/surgical intervention (eg, lack of housing, economic inadequacy, caregiver respite, family circumstances, administrative reason).
- Admission for administration of anticancer therapy in the absence of any other SAES

7.4 Routine Adverse Event Reporting

Investigators will assess the occurrence of AEs and SAEs at all participant evaluation time points during the study.

All AEs and SAEs whether reported by the participant, discovered during questioning, directly observed, or detected by physical examination, laboratory test or other means, will be recorded in the participant's medical record and on the appropriate study-specific case report forms.

The descriptions and grading scales found in the CTEP Active Version of the NCI Common Terminology Criteria for Adverse Events (CTCAE version 4.0) will be utilized for AE reporting. The CTEP Active Version of the CTCAE version 4.0 is identified and located on the CTEP website at:

http://ctep.cancer.gov/protocolDevelopment/electronic_applications/ctc.htm.

All appropriate treatment areas should have access to a copy of the CTEP Active Version of CTCAE.

All Adverse Events **must** be reported in routine study data submissions to the Overall PI on the toxicity case report forms. **AEs reported through expedited processes (e.g., reported to the**

IRB, FDA, etc.) must also be reported in routine study data submissions.

7.4.1 Routine Adverse Event Reporting to BMS

Adverse Events that are routinely collected according to GCP shall be submitted to BMS every three (3) months by the last working day of the third month.

The Adverse Event information required to be sent to BMS is noted in the ‘Bristol-Myers Squibb Early Asset Investigator Sponsored Research (ISR) Import Plan’ spreadsheet and submitted to BMS via the mailbox: [contact]

When the file is submitted to BMS, it must be noted that the file contains all “Non Serious Adverse Events” (only adverse events not previously submitted to BMS within the 3 months)

Sites other than Dana-Farber must fill out the ISR spreadsheet to Dana-Farber every three months and Dana-Farber will include information from other sites in their submissions to BMS.

7.5 Serious Adverse Event Collection and Reporting

Following the subject’s written consent to participate in the study, all SAEs, whether related or not related to study drug, must be collected, including those thought to be associated with protocol-specified procedures. All SAEs must be collected that occur within 100 days of discontinuation of dosing. All SAEs should be followed to resolution or stabilization.

All SAEs must be collected that occur during the screening period. If applicable, SAEs must be collected that relate to any protocol-specified procedure (e.g., a follow-up skin biopsy). The sponsor-investigator should report any SAE that occurs after these time periods that is believed to be related to study drug or protocol-specified procedure.

The sponsor-investigator will reconcile the clinical database SAE cases (case level only) transmitted to BMS Global Pharmacovigilance ([name]). Frequency of reconciliation should be every 3 months and prior to the database lock or final data summary. BMS GPV&E will email, upon request from the Investigator, the GPV&E reconciliation report. Requests for reconciliation should be sent to [contact]. The data elements listed on the GPV&E reconciliation report will be used for case identification purposes. If the Investigator determines a case was not transmitted to BMS GPV&E, the case should be sent immediately to BMS.

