7.6 Expedited Adverse Event Reporting to Overall PI

Investigators **must** report to the Overall PI any serious adverse event (SAE) that occurs following the subject’s written consent, during treatment, or within 100 days of the last dose of treatment on the local institutional SAE form.

In the event of an unanticipated problem or life-threatening complications, treating investigators must immediately notify the overall PI.

Investigators will report AEs directly to the DFCI Office for Human Research Studies (OHRS) per the DFCI IRB reporting policy, using the local institutional SAE form.

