10. STUDY CALENDAR

Screening evaluations are to be conducted within 3 weeks prior to study registration. Procedures done within a week of study registration don't need to be repeated to establish baseline. Scans and x-rays must be done ≤ 4 weeks prior to the start of therapy. Laboratory evaluations do not need to be repeated to meet eligibility criteria on cycle 1 day 1, if they were done within 3 days of the first treatment dose. In an event that the participant's condition is deteriorating, laboratory evaluations should be repeated within 48 hours prior to initiation of the next cycle of therapy. Each treatment cycle in this study is 28 days long.

Assessments must be performed prior to administration of any study agent. Study assessments and agents should be administered within ± 3 days of the protocol-specified date, unless otherwise noted.

	Screening	Window Phase	Pre-surgery	Surgery	Adjuvant phase							End of Treatment	Follow up visit 30 days after last dose
					Cycle 1		Cycle 2		Cycle 3		Cycle 4-6		
					Day 1	Day 15	Day 1	Day 15	Day 1	Day 15	Day 1		
Informed consent	X												
Medical History	X												
Concomitant Medicines	X												
Physical exam (Ht, Wt, VS, PS) ^a	X	X			X	X	X	X	X	X	X	X	X
Routine labs ^b	X	X			X	X	X	X	X	X	X	X	X
FSH (if female <55 years old)	X												
HPV testing (oropharyngeal only)	X												
B-HCG (WOCBP only) ^c	X									X	X		
ECG	X									X	X		

Radiologic evaluation ^{d, g}	X		X	X								
Biopsy sample ^{e, f}	X										X ^h	
Correlative biopsy ^f	X										X ^h	
Correlative blood ⁱ	X ⁱ					X					X	
Nivolumab		X		X	X	X	X	X	X	X		
Lirilumab		X		X		X		X		X		
Adverse event evaluation		X		X	X	X	X	X	X	X	X	X

- a) Physical exam is symptom directed. Height measured at screening only.
- b) Routine labs include: CBC, LFTs, CMP, Mg, TSH, Free T4. Baseline HCV antibody, hepatitis B surface antigen, hepatitis B surface antibody, and hepatitis B core antibody testing is required. TSH and free T4 are required less frequently according to the following schedule: screening, window phase (D1 of pre-surgery immunotherapy dosing), D1 of each adjuvant cycle, and at the 30-day post protocol treatment visit.
- c) Serum or urine within 24 hours prior to first dose.

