- d) PET-CT or contrast-enhanced CT imaging of the chest, abdomen and pelvis will be obtained at baseline to rule out distant disease. Contrast-enhanced neck CT or MRI at the time of screening or registration and will be repeated 1-4 days prior to salvage surgery. Interval scans (contrast-enhanced neck CT or MRI) will be performed every 8 weeks following salvage surgery or as clinically indicated while on treatment. Follow-up imaging will be performed at the end of treatment (see footnote g).
- e) Archival tissue is acceptable. Some of this tissue will also be used for correlative study.
- f) Fresh biopsy is mandatory if tumor is accessible. Fresh tissue is also collected at the time of surgery. Biopsy will also be obtained at the time of progression or recurrence, if safe to perform.
- g) Participants, regardless if they receive the adjuvant therapy, will be followed for response (at the end of the window phase of the trial) until first disease progression or recurrence and for survival throughout the trial for a total of 5 years from time of salvage surgery (or from study registration if no salvage surgery was performed). Post-end of protocol treatment, if first disease progression or recurrence has not been confirmed, tumor assessments (contrast-enhanced neck CT or MRI and PET-CT) are to continue every 3 months (+/- 1 month) until first disease progression or recurrence, death, or 2 years post-date of salvage surgery (or from study registration if no salvage surgery was performed), then every 6 months until 5 years post-date of salvage surgery (or from study registration if no salvage surgery was performed). After first disease progression or recurrence has been confirmed, patients will be followed for survival by phone only, every 3 months (+/- 1 month) until death or 5 years post-date of salvage surgery (or from study registration if no salvage surgery was performed), whichever occurs first.
- h) Recommended in the setting of disease recurrence or progression only.
- i) Screening correlative blood collection may occur at screening or at pre-surgery. Pre-surgery correlative blood collection may occur any time from the day following neoadjuvant drug administration until surgery. EOT blood draw may occur after the EOT visit.

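### SAEs must be collected to day 100 after the last dose, but no scheduled contact asks about days 31 to 100 once a patient has recurred

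*Combined protocol and SAP*

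**What the plan says.** **Collection window.** Section 7.5 requires all SAEs, related or not, to be collected after consent, and sets the end of the window: "All SAEs must be collected that occur within 100 days of discontinuation of dosing". Section 7.6 repeats the limit for reports to the Overall PI: "during treatment, or within 100 days of the last dose of treatment on the local institutional SAE form". Later events remain reportable if thought related (Section 7.5): "The sponsor-investigator should report any SAE that occurs after these time periods that is believed to be related to study drug or protocol-specified procedure".

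**Calendar.** In Section 10 the adverse event row is marked at the window phase, the adjuvant visits, End of Treatment, and the final column, "Follow up visit 30 days after last dose". There is no later column.

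**Contacts after treatment.** Footnote g to the calendar splits patients by recurrence. Without recurrence, tumor assessments "are to continue every 3 months (+/- 1 month) until first disease progression or recurrence, death, or 2 years post-date of salvage surgery", and six-monthly after that. After confirmed recurrence, "patients will be followed for survival by phone only, every 3 months (+/- 1 month) until death or 5 years".

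**General rule.** Section 7.4 states: "Investigators will assess the occurrence of AEs and SAEs at all participant evaluation time points during the study".

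**Analysis.** Evaluation of toxicity is in the first-listed secondary objective (Section 1.3). Section 13 says that adverse event frequencies will be summarized, without a cut-off day.

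**The concern.** The protocol sets a mandatory 100-day window but schedules active safety enquiry for only the first 30 days of it. What happens in the other 70 days depends on whether the patient has recurred. A patient without recurrence returns for scans and should be asked about adverse events there. A patient with recurrence receives calls whose stated purpose is survival. Recurrence is also a reason to stop treatment (Sections 5.2 and 5.6), so patients who recur on treatment enter survival-only follow-up while their 100-day window is still running.

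At stake is the completeness of the SAE summary for a new adjuvant combination, and whether completeness depends on disease outcome. A survival call will find a death. It need not find a hospitalization or another serious event that the patient survived.

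**Working it through.** The plan gives no figure for this point, so the check is a comparison of windows plus a sizing of the group affected.

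**1. Days without a scheduled adverse event evaluation**
- Required window: 100 days (Sections 7.5 and 7.6). Last calendar evaluation: day 30 (Section 10).
- 100 - 30 = 70 days (days 31 to 100).

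**2. Does the next contact close the window?**
- Interval: 3 months +/- 1 month (footnote g). The starting point of the interval is not stated.
- With 30.44 days per month: 2 x 30.44 = 61, 3 x 30.44 = 91 and 4 x 30.44 = 122 days.
- Counted from the last dose, the first contact falls on about days 61 to 122, nominally day 91, so it can come before day 100.
- Counted from the end of cycle 6, which is 28 days after a last dose on Day 1 of that cycle, it falls on about days 89 to 150, nominally day 119.
- For patients without recurrence, a further contact follows about 3 months later and can look back over whatever remained open.

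**3. Who is asked about SAEs after day 30?**

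| Patient | Contact after the 30-day visit | Is SAE enquiry required there? |
|---|---|---|
| No recurrence | Tumor assessment every 3 months | Yes, if Section 7.4 is read as covering these assessments |
| Confirmed recurrence | Phone call every 3 months | Not stated; footnote g limits it to survival |

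**4. Size of the recurred group**
- Inputs from Section 13: null 1-year DFS of 57%; 30% hazard reduction; 54 patients who have salvage surgery and begin adjuvant treatment.
- The plan's hazards reproduce: -ln(0.57) = 0.5621 per year; 0.7 x 0.5621 = 0.3935 per year.
- The 54 are counted from the start of adjuvant treatment, so the clock starts there. Six cycles x 28 days = 168 days = 24 weeks.
- Alternative hazard: 1 - exp(-0.3935 x 24/52) = 16.6%; 0.166 x 54 = 9.0.
- Null hazard: 1 - exp(-0.5621 x 24/52) = 22.8%; 0.228 x 54 = 12.3.
- So about 9 to 12 of 54 have a DFS event during the cycles. DFS events include deaths and invasive second primaries (Section 11.1.6), while phone-only follow-up starts at progression or recurrence. The figure is therefore an upper bound on those who move to phone-only follow-up during the cycles.
- Patients who first recur after the cycles but within 100 days of the last dose would join this group for the rest of their window. They are not in the 9 to 12.

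**The case against.** The strongest reply is that nothing here is contradictory. The duty in Sections 7.5 and 7.6 is unconditional, and the calendar does not cancel it. Calendar marks are not a full list of duties: concomitant medicines are marked only at screening, yet Section 5.5 requires all concurrent drugs to be captured. Section 7.4 covers events found by questioning, examination, laboratory test or other means. Most SAEs are deaths, life-threatening events or hospitalizations, which are hard to miss. SAE cases are reconciled with the drug supplier every 3 months and before database lock (Section 7.5). Patients stopped for toxicity are followed until the event resolves or stabilizes (Section 5.7). The End of Treatment and 30-day visits carry no exemption for recurrence.

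Much of this stands. For patients without recurrence, Section 7.4 and repeated 3-monthly assessments largely cover the window. Recurred patients are evaluated to day 30, and the obligation to day 100 applies to everyone.

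It does not answer the case of the recurred patient after day 30. Footnote g gives the call a single purpose, and nothing says that a survival call is an evaluation time point under Section 7.4. Reconciliation compares cases that are already recorded and does not ask patients about new ones. Follow-up under Section 5.7 concerns the event that stopped treatment.

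A reader might go further and infer that late toxicity is under-ascertained, that reported toxicity will be too low, or that late events surface only if volunteered. The documents do not support this. They give no late-event rate and no evidence of missed events, and the duty to collect remains. Nor does the nivolumab half-life in Section 2.2.1.1 help: persistence of drug after day 30 says nothing about how many events go unrecorded.

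**Conclusion.** The point holds as a mismatch between a mandatory window and the contacts meant to deliver it. SAE ascertainment over days 31 to 100 is unscheduled. In recurred patients it relies on passive reporting, because footnote g restricts their calls to survival. The result is a risk of incomplete SAE capture that differs by recurrence status, not a demonstrated loss of events.

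The sizing of 9 to 12 of 54 rests on exponential DFS at the plan's two hazards, a clock starting at adjuvant treatment, and 24 weeks of cycles. It counts patients exposed to the gap, not missed SAEs. The number of missed SAEs cannot be estimated from the documents.

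The primary DFS analysis is unaffected. With one arm there is no between-arm comparison to bias. What is exposed is the SAE part of the secondary toxicity objective. It is worth correcting because it concerns safety and the correction is easy.

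**What to change.** Reconcile Sections 7.5 and 7.6 with Section 10:

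1. Add an SAE check to the calendar at the first contact on or after day 100 from the last dose, for every treated patient, including those who have recurred and those who received only the window dose. Use the existing 3-monthly scan visit or phone call. Day 100 lies inside the present +/- 1 month tolerance whether the interval runs from the last dose (days 61 to 122) or from the end of cycle 6 (days 89 to 150), so that contact can usually be booked on or after day 100 without adding one.
2. Amend footnote g so that this call covers SAEs as well as survival, and state the date from which the 3-month interval is counted.
3. In Section 13, report SAE frequencies through day 100 and state the cut-off for non-serious AEs, which is the 30-day visit as now scheduled. The 100-day rule covers SAEs only, so extending all AE tables to day 100 would go beyond what the protocol requires.

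The cost is a slightly longer scripted contact per patient. Reported SAE counts may rise and may include events after subsequent therapy, so the start of any such therapy should be recorded beside the event.
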